#### **Informed Consent Process:**

All patients who meet the criteria for enrollment in the study will be given both a verbal as well as written detailed explanation of what participation will entail. They will be spoken to in English or Maltese, depending on what their preferred language is and information letters will also be available in both languages. They will be asked to sign a consent form prior to enrollment in the study. Should they wish to ask any further questions or request clarification regarding their involvement in the study at any point during the study, one of the researchers will be available to provide the information they require.

#### **Special Considerations for Persons who are Unable to Consent:**

In the case of persons who are unable to provide informed consent, the legal carer will be approached for purposes of consent and will be asked to be present with the participant throughout the study session. Questions will be directed at the participant as much as possible but carers will be asked to provide information that participants cannot provide, should they feel comfortable doing so. Participants have a right to refuse to participate in any test or questionnaire that they do not wish to participate in, and carers also have the right to stop patients' participation in any test or questionnaire they feel is inappropriate for the person. In the case that the person regains their capacity to consent for themselves, they will be asked to confirm consent to participate in the study or have their data

removed, although this may not be possible for data that has been included in analysis and publication.

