**Sample Size:**

From the patients discharged from ITU over the months of September 2020 up until April 2021, we are predicting approximately 100 patients to have survived beyond 6 months after discharge from the unit. These will all be offered inclusion in the study.

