**Secondary Objectives:**

Specific objective 1:

Observation of the long-term organ failures and medical conditions as a sequela of acute critical illness with COVID-19.

Specific objective 2:

Observation of the effect critical illness due to COVID-19 has on a patients' physical health, mental health and health related quality of life at 6 and 12 months after discharge from the ICU.

Specific objective 3:

Observation of how different severity of critical illness secondary to COVID-19 infection correlates with medium and long-term health related quality of life outcomes.

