### **Study design/methodology**

An observational cohort study of patients discharged from the ICU following admission with COVID-19 infection.

All patients discharged from the intensive care unit after a diagnosis of COVID-19 infection will be contacted by phone by one of the members of the research team listed below at six and twelve months after discharge. They will be asked to attend a follow-up appointment at the Pre-Operative Assessment Clinic in Mater Dei Hospital. They will be alone in the room with a researcher to protect their privacy, but they may request to have a person of their choosing such as a relative with them during the interview, if they so wish. For patients unable to attend the hospital appointment, an offer will be extended to perform the interview at their place of residence.

Participants will be asked a number of questions taken from validated questionnaires, namely the Hospital Anxiety and Depression Scale, the Barthel Index and the RAND 36-Item Health Survey. These questionnaires aim to establish the patient's own perception of his or her health, both physical and mental, his or her ability to perform daily activities alone or with help, and the patient's feelings about whether their health has changed since prior to their hospital admission and if so, in what way.

A physical examination will be offered to participants which includes examination of the heart and lungs by auscultation, and recording of height and weight as well as resting blood oxygen saturation via pulse oximetry.

Patients will also be asked to perform a six-minute walk test, if they feel they are able to. This essentially involves walking on a treadmill while clinical non-invasive monitoring such as ECG electrodes, a pulse oximeter and a blood pressure cuff are attached to monitor the vital signs during exercise. The test will be stopped if the patient requests this or if the researcher finds evidence that the patient is unfit to continue the test.

Pulmonary function testing will also be offered. This test would involve breathing through a specialised tube that calculates the flow rates that the patient is able to generate, both during normal breathing as well as during deep breathing. Once again, trained professionals will be performing this test and it will be stopped if the patient requests this or if the health professional deems the patient unfit to proceed with the test.

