#### **Analysis Plan:**

Data analysis will initially be quantitative, regarding number of patients surviving beyond 6 months after discharge from ITU following their critical illness with COVID-19. Their residential arrangements following discharge will also be noted (care home or private residence).

Following this initial analysis, results of validated questionnaires which will be used to assess the patients, will be reviewed and this data will be compared to data from other studies regarding the general public of similar age groups as well as persons discharged from ITU after critical illness due to causes other than COVID-19. Their physical assessment (6 minute walk test) and pulmonary function test results will also be analyzed and compared to normal ranges for persons in their age group.

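### Carer answers may enter scales meant to record the patient's own perception, with no record of who answered; this could bias the severity–quality of life association in either direction

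*Combined protocol and SAP*

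**What the plan says.** The section on persons unable to consent sets the rule: questions go first to the participant, and "carers will be asked to provide information that participants cannot provide". It does not say which instruments or items a carer may answer. Its later sentences give participants and carers rights over any test or questionnaire, so the questionnaires fall within its scope.

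The Study design/methodology section names the instruments as "the Hospital Anxiety and Depression Scale, the Barthel Index and the RAND 36-Item Health Survey" and states their purpose: "These questionnaires aim to establish the patient's own perception of his or her health, both physical and mental". It adds ability in daily activities and the patient's feelings about change in health.

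Specific objective 3 under Secondary Objectives is "Observation of how different severity of critical illness secondary to COVID-19 infection correlates with medium and long-term health related quality of life outcomes".

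The Analysis Plan treats the questionnaires as one body of data: "results of validated questionnaires which will be used to assess the patients, will be reviewed and this data will be compared to data from other" (quotation cut short; the sentence goes on to name outside research in the general public and in other ICU survivors). It mentions no respondent variable, stratification, adjustment or sensitivity analysis. The Sample Size section forecasts the cohort: "we are predicting approximately 100 patients to have survived beyond 6 months after discharge from the unit". Storage of Data provides for deletion of all data once analysis is complete.

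**The concern.** The stated purpose of the scales and the rule on carers do not fit together without a further provision. An anxiety, depression or perceived-health item answered by a carer is a different measurement from the same item answered by the patient. The problem is weaker for the Barthel Index, because a carer can observe daily activities.

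A few carer answers spread evenly over the cohort would matter little. The risk arises if they cluster at one end of the severity range. Respondent and severity are then confounded, and a difference in reporting can appear as a difference in quality of life. Objective 3 is the most exposed. The comparison with published self-report data is also affected, though less.

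Without a respondent record, nobody could later tell whether the bias was upward, downward or nil. Once the data are deleted, the question could not be reopened.

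**Working it through.** **The plan's own figure.** The only relevant number is the forecast of about 100 survivors. It comes with no alpha, power, effect size or SD, so there is no calculation to reproduce.

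**Assumptions.** None of these is in the documents.
- Severity S is standard normal. The self-reported score is ρS + error with variance 1, and lower means worse. For a scale where higher means worse, the signs reverse.
- A share q of questionnaires is carer-answered, with q from 0.05 to 0.15. These are a random half of the most severe 2q of the cohort.
- A carer answer shifts the score by d, from 0.3 to 0.5 SD. Formulas are written for carers rating worse; if they rate better, d is negative.

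**Formulas.** Let z be the cut-off with P(S > z) = 2q. The covariance of severity with carer response is c = 0.5 × φ(z). Then:
- Cov(S, Y) = ρ − d·c
- Var(Y) = 1 + d²q(1 − q) − 2dρc
- r = Cov(S, Y) / √Var(Y)

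**Low corner, q = 0.05 and d = 0.3.** c = 0.0877.
- ρ = 0: r = −0.0263/√1.0043 = −0.026.
- ρ = −0.20, carers worse: r = −0.2263/√1.0148 = −0.225.
- ρ = −0.20, carers better: r = −0.1737/√0.9937 = −0.174.

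**High corner, q = 0.15 and d = 0.5.** c = 0.1738.
- ρ = 0: r = −0.0869/√1.0319 = −0.086.
- ρ = −0.20, carers worse: r = −0.2869/√1.0666 = −0.278.
- ρ = −0.20, carers better: r = −0.1131/√0.9971 = −0.113.

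With ρ = 0 and carers rating better, the same sizes appear with a positive sign.

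**Shift in the overall mean.** This is q × d: 0.05 × 0.3 = 0.015 SD, up to 0.15 × 0.5 = 0.075 SD.

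**Rare proxy use.** At q of 0.01 to 0.02 and ρ = 0, carers rating worse give r from −0.007 to −0.021.

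**A different model of proxy use.** A simulation let the odds of a carer answer rise with severity, by a ratio of 2 to 4 per SD, with shares of 5–20%.
- Carers 0.5–0.8 SD worse: a true 0 becomes −0.015 to −0.13, and a true −0.20 becomes −0.21 to −0.31.
- Carers 0.5 SD better: a true −0.20 shrinks to −0.18 to −0.11.
- Odds ratio 1, so proxy use unrelated to severity: a true 0 stays at 0.00, and a true −0.20 stays at −0.19 to −0.20.

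**Scale against sampling error.** At n = 100 the 95% margin on a correlation near zero is about 1.96/√97 = 0.20. By the Fisher z approximation, the chance of p < 0.05 with no true link rises from 5% to about 5.8% at the low corner and 13.5% at the high corner.

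**Self-report only.** In the first model, dropping carer-answered questionnaires turns a true −0.20 into −0.187 (q = 0.05) or −0.185 (q = 0.15), because the severity range narrows.

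**The case against.** The protocol never says outright that carer answers are scored into the Hospital Anxiety and Depression Scale or RAND-36. It directs questions to the participant first, lets carers stop a questionnaire they find inappropriate, and lets either party decline questions. The absence of a respondent record is inferred from a short protocol without a case report form. This stands as a limit on certainty. Scoring carer answers remains the natural reading, and none of these safeguards identifies the answers that carers do give.

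A reader might infer that carer answers will create or inflate a link between severity and poor quality of life. The documents do not support that. They do not define severity, do not say how many participants lack capacity, and do not say why; incapacity could predate COVID-19. Nor do they say whether carers rate better or worse than patients would. If carers rate better, a true link shrinks.

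The bias is also modest. Under these assumptions it is well inside the sampling margin at n = 100, and the Analysis Plan specifies neither a significance test nor a severity analysis. That last omission is a larger, separate matter. The objection fairly limits the importance of the point, but objective 3 is still a stated aim.

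Finally, a reader might conclude that self-report should be the main analysis. That choice has its own cost: it leaves out patients without capacity and slightly attenuates a true association.

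**Conclusion.** The point holds as a gap in recording and reporting. Following the plan could mix two kinds of measurement in the two subjective scales, with no means of separating them afterwards. Under the assumed 5–15% share and 0.3–0.5 SD gap, concentrated in the most severe patients, the correlation in objective 3 moves by roughly 0.02 to 0.09. The direction depends on how carers rate and is unknown. The effect on the overall mean is at most 0.075 SD. Both effects are small if proxy use is rare, and the correlation hardly changes if proxy use is unrelated to severity.

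The documents support neither a claim of inflation nor a ruling that self-report must be primary. Cheap improvement.

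**What to change.** In the section on persons unable to consent, add that the respondent (patient, carer or both) is recorded for each questionnaire at each visit. Any questionnaire with carer-answered items counts as both or carer. Recording at each visit matters because the protocol foresees that a participant may regain capacity.

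In the Analysis Plan, add three statements:
- The number of carer-assisted cases and their severity will be reported.
- Hospital Anxiety and Depression Scale and RAND-36 results will be presented both with and without carer-assisted questionnaires.
- Barthel Index answers from either source will be pooled.

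The cost is one tick box per questionnaire and one extra analysis. A record at questionnaire level does not show which items the carer answered. The self-report-only result omits patients without capacity, so neither result should be read alone.

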**Refusal or Withdrawal of Data:**

All participants and their carers are at liberty to refuse to participate in all or part of this research study. Participants and carers may refuse to answer any questions they are uncomfortable with, and may refuse to take any physical test that they do not wish to take. They may also ask to stop their participation in any questionnaire or physical test at any point in time. Participants or their carers may also ask for their data to be deleted after its collection, but should be aware that this may not be possible for data that has already been included in statistical analysis and publication. Refusal to participate in all or part of the study, or withdrawal of data after participation will not result in any loss of benefits and will not incur any penalties or liabilities. Participation is voluntary and any refusal to participate by the patient or guardian will not have any effect on the person's care pathway within the hospital.

**Privacy and confidentiality:**

**Storage of Data:**

All data collected in this study will be stored on MITA Sharepoint after anonymisation by use of a code. This is the official Mater Dei Hospital server for data storage and ensures security of the stored data. All data will be deleted after analysis of all gathered data is complete. A specific date for this cannot be given since the pandemic is an ongoing evolving situation.

**Processing of Data:**

Data will be analysed after collection is complete to extract statistical information about the long-term health effects of severe COVID-19 infection requiring intensive care admission. This data may be published in scientific journals at a later stage and shared with colleagues for instructional purposes. All data will be anonymised and no data which can lead to personal identification will be shared or published.

**Data Accessibility:**

The stored data will be accessible only to members of the research team whose names and email addresses are printed below.

Refusal or Withdrawal of Data: All participants are at liberty to refuse to participate in all or part of this research study. Participants may refuse to answer any questions they are uncomfortable with, and may refuse to take any physical test that they do not wish to take. They may also ask to stop their participation in any questionnaire or physical test at any point in time. Participants may also ask for their data to be deleted after its collection, but should be aware that this may not be possible for data that has already been included in statistical analysis and publication. Refusal to participate in all or part of the study, or withdrawal of data after participation will not result in any loss of benefits and will not incur any penalties or liabilities. Participation is voluntary and any refusal to participate will not have any effect on the person's care pathway within the hospital.

**Risk/Benefit:**

**Risk to participants:**

No risks to participants are foreseen as a direct result of this research study.

**Benefits to Participants**

The results of this research will contribute to a better understanding of the consequences of severe COVID-19 illness on patients several months after the resolution of their illness, and may help shape services to help these patients after their discharge from hospital.

Patients will benefit from referral to appropriate specialist outpatient clinics if our assessment reveals that they will benefit from this, and the participant is willing to attend.

**Study Timeline:**

Stage 1 - Screening and enrolment of participant - 1 month

Stage 2 - Data collection (interviews and physical assessment) – 1 year

Stage 3 - Data analysis – 3 months

Stage 4 - Presentation and publication

**Conflict of Interest:**

The investigators and researchers have no conflict of interest to declare.

